*Rigor of the prior research:* To our knowledge, there are no studies examining the impact of coffee or caffeineinduced natriuresis on intrarenal hemodynamic function and renal energetics in youth with T1D. Our preliminary data suggest that coffee intake protects against acute kidney injury (see below), and recent findings from the UK Biobank reports an inverse relationship between caffeinated and non-caffeinated coffee drinking and mortality (32). Therefore, the UK Biobank data strongly support the importance of noncaffeine constituents in the coffee-mortality association (32). Consistent with these data, recently published data also demonstrate that daily coffee intake is associated with decreased risk of development of chronic kidney disease {Jhee, 2018 #15851}. Accordingly, it is important to evaluate the effect of coffee rather than simply caffeine on intrarenal hemodynamic function and energetics (oxygenation). In addition, brews are thought to

contain a higher number of bioactive compounds including polyphenols than instant coffee (40). Further, cold brews are proposed to retain the bioactive compounds better through their slower brewing process compared to hot brews (41).

Our overall hypothesis in this pilot and feasibility trial is that cold brew coffee drinking for 7 days improves renal oxygenation by reducing renal O_2 consumption, without impairing GFR and ERPF (**Fig 2**).

[figure not shown]

Fig 2 Proposed Mechanism of Coffee Drinking on Renal Function

Impact: Clinical trials in DKD have yielded disappointing results for the past two decades. This trend may be explained in part by the lack of understanding around what initiates early DKD, and by failing to intervene at the initial stage of the disease when benefit may be maximally achieved. This proposal seeks to investigate the effect of coffee on intrarenal hemodynamics, renal perfusion and oxygenation in youth-onset T1D. Given the global diabetes and obesity epidemic, the ability to potentially reduce renal O₂ consumption and increase renal oxygenation without the TGF-mediated reduction in ERPF and GFR, provides a strategic approach to reduce the huge burden of DKD, a major cause of morbidity and premature mortality. This pilot and feasibility study will provide preliminary data and direct a larger clinical trial.

III. Preliminary Studies/Progress Report:

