Visit 1 (Screening visit): Prescreening will be done by phone or in conjunction with a clinical diabetes visit. The full screening visit will include the consent process, history, allergies confirmed, physical exam, and screening labs (HbA1c, hemoglobin and hematocrit [H&H], serum creatinine, urine microalbumin to creatinine ratio). All females will also have a pregnancy test and detailed menstrual history. The screening visit will take approximately 2 hours.

Visit 2, part 1: Participants will present the evening before the study visit, or present fasting to the Pediatric CTRC in the morning, and have IV(s) placed. Fasting blood will be drawn for serum copeptin, lipids, insulin, cystatin c, creatinine, sodium, hematocrit and total protein prior to the clamp. Participants will be escorted to the Brain Imaging Center or CHC Radiology for a BOLD and ASL MRI per local protocol. BOLD MRI measurements will be performed at baseline and following administration of a small dose of furosemide (20 mg IV) via the PIV. A study physician or nurse will be responsible for the furosemide administration. Total duration of part 1 will be approximately 1.5 hours.

Visit 2, part 2: Participants return to pediatric CTRC and will have their blood glucose concentrations clamped in the hyperglycemic range. Participants will also undergo iohexol and PAH clearance studies, in addition to 4-hour urine collection for album excretion rate (AER) and albumin to creatinine ratio (ACR). Upon completion of visit 2, participants will be provided with a study meal (lunch). After lunch, participants will undergo DXA scan for quantification of body composition. This concludes the study. Total duration 6 hours.

Post-coffee visit (COFFEE Study):

Visit 3, Part 1: Participants will present the evening before the study visit, or present fasting to the Pediatric CTRC in the morning, and have IV(s) placed. Fasting blood will be drawn for serum copeptin, lipids, insulin, cystatin c, creatinine, sodium, hematocrit and total protein prior to the clamp. Participants will be asked to drink 1 bottle of Starbucks® Cold brew before being escorted to the Brain Imaging Center or CHC Radiology for a BOLD and ASL MRI per local protocol. BOLD MRI measurements will be performed at baseline and following administration of a small dose of furosemide (20 mg IV) via the PIV. A study physician or nurse will be responsible for the furosemide administration. Total duration of part 1 will be approximately 1.5 hours.

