is not radioactive (e.g. iothalamate renography at CHCO). The dose to be used in this study is 10-50 times less than that used in radiology studies. Our protocol has been adapted from that used by the RASS study where they reported only minor allergic reactions in over 1,200 iohexol studies performed in over 200 adults with type 1 diabetes in that study. Principal investigator, [name], has performed iohexol studies in adolescents with type 1 diabetes at Barbara Davis Center for Diabetes (62) which was well tolerated without any reactions. Furthermore, collaborator [name] has at least 10-year experience with iohexol studies in both pediatrics and adults with and without type 1 diabetes. To further limit risk of allergic reactions, patients with an allergy to iodine, seafood or iohexol will not be allowed to participate. Rare adverse effects associated with iohexol in radiology studies include cardiac arrhythmias (an irregular heartbeat), headaches, blurred vision, and nausea. To reduce risk of contamination, single use vials will be used.

PAH infusion: PAH (University of Minnesota) has been used to measure RPF in human research for decades and is very well tolerated and generally recognized as safe with low toxicity. Collaborator, [name] has infused PAH in children and adults with and without T1D for the last 10 years without any significant reactions (38, 55, 60, 62, 64, 79-81). PAH was previously approved by the FDA as the gold standard to quantify RPF. As the prior manufacturer, Merck, no longer supplies PAH, [name] has submitted an IND application to use PAH produced by University of Minnesota in this study as an investigational product (IND #140129). To minimize risk, a sterile preparation is used and prepared by the pharmacy using sterile techniques. Furthermore, single use vials will be used to reduce risk of contamination. However, as with any infusion, there is the possibility of infection, and the possibility of an allergic reaction. In the event of an allergic reaction, the study will be discontinued, and the participant will be treated.

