Coffee therapy: The caffeine dose of 205 mg (1 bottle) during the 6 days prior to the post-intervention visit is consistent with quantities used in previous studies, typically ranging between 200-400 mg (49-55). During the post-intervention visit, the 7th day, the participants will also receive 1 bottle of Starbucks® Cold brew. These doses are less than the 400mg/day considered safe in non-pregnant subjects and not associated with adverse effects in terms of acute toxicity, cardiovascular toxicity, bone and calcium effects, behavior, and development and reproduction (53-56).

While caffeine at the doses used in this study is considered safe for most people, we will warn participants of the following possible side-effects including insomnia, nervousness and restlessness, stomach irritation, nausea and vomiting, increased heart rate and respiration, headache, anxiety, agitation, chest pain, and ringing in the ears. If the participants develop any of these symptoms we will ask them to only drink ½ bottle, and if symptoms persistent we will withdraw them from the study. We will further reduce the risk of these side effects based on the dosing schedule in the morning and avoiding higher doses which increases risk for unpleasant side effects. Too much caffeine may worsen arrhythmias, insomnia, tremors, tics, generalized anxiety disorder, bipolar disease, panic attacks, Tourette's, epilepsy or overactive bladder. Participants with these conditions will be excluded. Participants with previous adverse reactions to coffee will also be excluded. Participants naïve to coffee and caffeine will also be excluded to prevent withdraw symptoms upon study completion. While caffeine is considered safe in pregnant and breast-feeding women when used daily amounts are less than 200-300 mg, we will exclude pregnant or nursing mothers due to the other procedures being performed in this study.

Study Diet: There is a small risk that blood sugars will be higher or lower than normal in subjects with diabetes at home while eating the recommended study diet as it may differ from the subject's usual diet. To avoid this risk, subjects will be asked to monitor their blood sugars frequently at home and will be called daily to review blood sugars. Carbohydrate content will also be provided for each food item to assist with carbohydrate counting.

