Confidentiality: Violation of privacy and loss of confidentiality are both risks to which research participants are exposed. The possibility of these risks increases when protected health information is collected. Every effort will be made to decrease this risk by limiting access to protected health information, storing this information in a password protected database, and identifying subjects only by a unique identifier that is kept in a separate location in a locked container, traceable only by study personnel. All tests involve risk of identifying asymptomatic/subclinical abnormalities. The study may also include risks that are unknown at this time of examination.

8. Plan to minimize risk / protection against risk:

The hyperglycemic clamps, iohexol and PAH infusions are standard procedures used in several research studies and settings, including our RENAL-HEIR protocol (COMIRB #16-1752), CASPER protocol (COMIRB #17-0820), IMPROVE-T2D protocol (COMIRB #18-0704). Adverse events are uncommon when the procedure is done by experienced personnel in an appropriate setting. There have been no Serious Adverse Events (SAE) in the research group's experience in the Pediatric Clinical and Translational Research Center with insulin clamps, iohexol or PAH clearance studies. Therefore, we do not anticipate encountering SAEs. However, we have defined the following as possible SAEs for the purposes of monitoring: infection related to blood draw or IV placement. In addition, allergic reactions to iohexol or PAH requiring intervention (e.g. oral Benadryl) would also be considered a SAE. The PI will report serious adverse events, and any decision to suspend or halt the protocol to the CTRC and COMIRB immediately. The subject will also be instructed to report the event to their PCP. Caffeine dosing less than 400mg/day considered safe in non-pregnant subjects and not associated with adverse effects in terms of acute toxicity, cardiovascular toxicity, bone and calcium effects, behavior, and development and reproduction (53-56). This is roughly the amount of caffeine in four cups of brewed coffee. We will also exclude caffeine-naïve participants to reduce the likelihood of withdrawal effects and exclude participants with prior adverse effects to caffeine, on other stimulants for ADHD, tremors, tics, Tourette's, arrythmias, insomnia and overactive bladder.

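### The coffee-symptom rule gives chest pain the same response as a headache: carry on with half a bottle, with no stop and no medical assessment

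*Combined protocol and SAP*

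**What the plan says.** The intervention is one 325 ml bottle of cold brew (205 mg caffeine) each morning for 6 days, with a seventh bottle on the morning of the post-intervention visit (section IV, Intervention).

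C.7, Coffee therapy, lists the side-effects participants will be warned about. The list includes insomnia, nausea and a faster heart rate, and it ends with "headache, anxiety, agitation, chest pain, and ringing in the ears". One rule then covers the whole list, for participants who "develop any of these symptoms we will ask them to only drink ½ bottle, and if symptoms persistent we will withdraw them". The paragraph goes on to exclude people with conditions that too much caffeine may worsen, arrhythmias among them, and people who have reacted badly to coffee before.

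Other safety provisions that bear on the point:

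- Visit 1: "The full screening visit will include the consent process, history, allergies confirmed, physical exam, and screening labs". The labs named are HbA1c, hemoglobin and hematocrit, creatinine and urine albumin-to-creatinine ratio. No ECG is listed.
- C.7, PAH infusion: "In the event of an allergic reaction, the study will be discontinued, and the participant will be treated".
- C.7, Study Diet: participants "will be called daily to review blood sugars".
- C.8: "we have defined the following as possible SAEs for the purposes of monitoring: infection related to blood draw or IV placement", and "allergic reactions to iohexol or PAH requiring intervention (e.g. oral Benadryl) would also be considered a SAE". C.8 also has the principal investigator report serious adverse events, with no limit by cause, to the research center and the IRB at once.

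**The concern.** A rule that halves the dose for any symptom suits headache, restlessness or stomach upset. It does not suit chest pain, where the usual order is to stop the exposure, assess, and then decide. Here the order is reversed: the written step is a further, smaller dose, and leaving the study depends on the symptom lasting.

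The protocol's own reasoning points to a stricter response. It treats arrhythmia as a reason not to give caffeine, but exclusion can only reach arrhythmias that are known or that come to light in the history and examination. An unrecognized one could first appear as a symptom on this list. Many participants will be minors, and for most doses no clinician is described as being present.

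What is at stake is the safety of an individual participant. No estimate or test depends on it.

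**Working it through.** The plan states no figure on this point, so the check is mainly a comparison of provisions.

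**1. What the rule does to the dose.** Inputs: 205 mg per bottle; 7 doses, 6 of them before the visit (section IV, Intervention). Half a bottle is 205/2 = 102.5 mg. If chest pain first appears after dose k, with k from 1 to 6, then 7 − k doses remain. If the pain does not persist, and the reduction carries through to the visit (the plan does not say), the participant takes between 1 (k = 6) and 6 (k = 1) further half bottles without any required assessment. After the seventh bottle there is nothing left to reduce, so the rule matters for symptoms arising before the visit.

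**2. Is there an exception elsewhere?** Responses written in the protocol:

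- PAH allergic reaction: discontinue and treat (C.7).
- Low glucose not corrected by two servings of juice: call the study physician and start dextrose (Hyperglycemic insulin clamp).
- Iohexol and PAH infusions: nurse and clinician at the bedside throughout (Iohexol clearance and PAH clearance).
- Any listed coffee symptom, chest pain included: half a bottle, then withdrawal if it persists (C.7).

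C.8 mentions caffeine only to describe the dose as safe and to repeat exclusions. The outcome list, Table 6 and section G add no response to coffee symptoms. No other section changes the instruction for chest pain.

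**3. How often it might matter.** The documents give no rate, so p is assumed. For 10 participants, P(at least one) = 1 − (1 − p)^10:

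- p = 0.5%: 1 − 0.995^10 = 4.9%
- p = 1%: 1 − 0.99^10 = 9.6%
- p = 2%: 1 − 0.98^10 = 18.3%

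**4. What a stricter rule could cost.** A stop may lose a pair of visits. For a paired t-test at two-sided alpha 0.05 (assumed; the plan states no alpha), the effect d detectable with 80% power solves P(T > t(0.975, n − 1)) = 0.80, where T is noncentral t with n − 1 degrees of freedom and noncentrality d√n. In units of the SD of the paired differences, this gives 1.00 at n = 10, 1.07 at n = 9 and 1.16 at n = 8. These values serve only to price a lost pair. The plan's stated 0.44 SD is a separate question.

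**The case against.** The best defense is that C.7 is a short risk paragraph setting a minimum response. It does not forbid a physician from assessing a participant or withdrawing one at once, and an experienced pediatric team probably would. The dose is below the 400 mg/day the protocol cites as safe, it is taken in the morning, and people new to caffeine, with earlier bad reactions or with known arrhythmias are excluded. The PAH contrast sets an intravenous investigational product against a retail drink. The screening summary comes from the parent CASPER study, whose full protocol is not supplied, so the missing ECG is weak evidence. The consent pages were not available and may say more.

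Most of this stands as a reason why the rule will seldom be used for chest pain. It does not alter what staff and families are told to do when it is. That chest pain calls for a stop is a clinical judgment rather than a statement in the documents, but it follows the protocol's own reason for excluding arrhythmia.

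Two stronger readings are tempting and not supported:

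- A reader might infer from the C.8 list that harm from coffee goes unreported or uncounted. That list is of possible serious events, and the general reporting sentence covers a serious coffee event. Reductions and withdrawals are steps that staff themselves take, and among 10 participants a withdrawal before the visit would show as a missing post-coffee visit. What remains is that non-serious coffee events have no stated place in the report. The undescribed questionnaires in Table 6 might even capture them.
- A reader might infer that the primary results are biased. Nothing here shows that. Section G does not say how a participant on half dose enters the paired analysis, but it makes the unadjusted comparison primary and calls the data hypothesis generating.

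**Conclusion.** The point holds in a narrow form. The written rule re-doses a participant who has chest pain, at 102.5 mg a day, with no stop and no assessment, and no other section corrects it. The chance of this arising at least once in 10 participants is about 5% to 18%, resting wholly on assumed rates of 0.5% to 2%. Rates for the whole symptom list would be higher, but they would mostly count complaints for which half a bottle is a reasonable response.

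This is a cheap improvement for patient safety. It is not a flaw in the analysis, and it does not show that serious harm would go unreported. Confidence is moderate, because the consent form and the full parent protocol were not seen.

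**What to change.** Split the rule in C.7, Coffee therapy:

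- **Chest pain:** stop the coffee. A study physician assesses the participant before any further bottle, and the participant is withdrawn if not cleared.
- **Increased heart rate:** treat as for chest pain only if the study physician judges it marked or symptomatic. It is a listed caffeine effect, and a mandatory stop with no threshold would be too broad.
- **Other listed symptoms:** keep the present rule.

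Optionally, ask about symptoms and the amount drunk at the daily call already planned, and report reductions and withdrawals descriptively. This suits a study of which the plan says: "This pilot and feasibility study will provide preliminary data and direct a larger clinical trial".

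The cost is a few lines of protocol text, a little physician time and the possible loss of a pair that half-dosing would have kept. Sample size, endpoints and primary test stay as they are.

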Caffeine, a methylxanthine, is known to alter kidney function by several mechanisms including natriuresis, hemodynamics and renin-angiotensin-aldosterone system (31). In contrast, to other natriuretic agents, caffeine is thought to fully inhibit the local tubuloglomerular feedback (TGF) response to increased distal sodium delivery. This observation has broad-ranging implications as caffeine can reduce renal oxygen (O_2) consumption without impairing effective renal plasma flow (ERPF) and glomerular filtration rate (GFR). There are also data suggesting that chemicals in coffee besides caffeine may provide important cardio-renal protection (32). Yet, there are no data examining the impact of coffee-induced natriuresis on intrarenal hemodynamic function and renal energetics in youth-onset T1D. Our overarching hypothesis in the proposed pilot and feasibility trial is that coffee drinking improves renal oxygenation by reducing renal O₂ consumption without impairing GFR and ERPF. To address these hypotheses, we will measure GFR, ERPF, renal perfusion and oxygenation in response to 7 days of cold brew coffee (one Starbucks® Cold brew 325ml bottle daily [205mg caffeine]) in an open-label pilot and feasibility trial in 10 adolescents with T1D already enrolled in CASPER Study (#17-0820, PI: [name]).

SA1: To evaluate the impact of 7 days of coffee drinking on renal perfusion and oxygenation in adolescents with T1D.

- H1: Coffee drinking will improve renal oxygenation and perfusion in adolescents with T1D.
- SA2: To evaluate the impact of 7 days of coffee drinking on intrarenal hemodynamic function and tubular injury markers in youth with T1D.

H2.1: Coffee drinking will not significantly change GFR and ERPF in youth with T1D.

H2.2: Coffee drinking will decrease concentrations of tubular injury markers in youth with T1D.

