II. Background and Significance: Over 1.25 million Americans have T1D, increasing risk for early death from cardiovascular disease (CVD) (33, 34). Despite advances in glycemic and blood pressure control, a child diagnosed with T1D is expected to live up to 17 years less than non-diabetic peers (1-4). The strongest risk factor for CVD and mortality in T1D is DKD (5, 6). Current treatments, such as control of hyperglycemia and hypertension, are beneficial, but only partially protect against DKD (7-14). This limited progress may relate to a narrow focus on clinical manifestations of disease, rather than on the initial metabolic derangements underlying the initiation of DKD (15). Renal hypoxia, stemming from a potential metabolic mismatch between increased renal energy expenditure and impaired substrate utilization, is increasingly proposed as a unifying early pathway in the development of DKD (21, 35, 36). T1D is impacted by several mechanisms which *increase renal ATP consumption* and *decrease ATP generation*.

Caffeine is known to modify renal function by several mechanisms including natriuresis, hemodynamics and renin-angiotensin-aldosterone system. Caffeine is also thought to inhibit the expression of the Na⁺/K⁺ ATP pump and isoform 3 of the Na⁺/H⁺ exchange; both are key proteins in the mechanism of active/passive tubular reabsorption (31). In contrast, to other natriuretic agents, caffeine is theorized to fully inhibit the local TGF response to increased distal Na⁺ delivery. This observation has broad-ranging implications as caffeine can reduce renal O_2 consumption (by inhibiting Na⁺ reabsorption which accounts for the majority of renal O_2 consumption) without impairing ERPF and GFR. Such mechanisms can provide protection from acute and chronic tubular and glomerular injuries. There are also important non-renal mechanisms hypothesized to explain the potential protective effect of coffee drinking on mortality including reduced inflammation, improved insulin sensitivity, and endothelial function (37-39).

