Potential scientific problems: In any clinical study, unforeseen human factors provide challenges. We have experience with hyperglycemic clamps, iohexol and PAH clearance studies and MRI methods in youth with T1D and have already obtained preliminary data. We anticipate an increase in renal oxygenation due to decreased renal oxygen consumption with preserved GFR and ERPF in response to coffee therapy. In addition, we expect decreased plasma concentration of tubular injury markers in response to coffee therapy. Clearance of PAH is the gold standard method to measure ERPF, and GFR by iohexol clearance is more accurate and precise than eGFR. Importantly, iohexol and PAH clearances do not interfere with the assessment of insulin sensitivity during a hyperglycemic clamp. Mild hyperglycemia (~ 190mg/dl) during the GFR measurements and a salt replete and protein controlled diet are critical strengths as severe hyperglycemia acutely increases GFR, and salt and protein intake influence intrarenal hemodynamics (97). Furthermore, mild hyperglycemia allows us to quantify intrarenal hemodynamic function in a glycemic milieu similar to their native pathophysiology. In contrast, a hyperinsulinemic-euglycemic clamp would render the participants completely normoglycemic, which does not reflect their usual glycemic environment, and expose them to high concentrations of insulin which may interfere with the assessment of their intrarenal hemodynamic function. Based on our preliminary work, we expect the 2 renal sequences (BOLD and ASL) to be completed within 60 min. In our other studies we have had adolescents with T1D, T2D and without diabetes undergo similar MRI procedures lasting 120 min, indicating that recruiting and tolerability in youth for such procedures are feasible. Our research MRI is equipped with in-MRI movie-viewing with noise-cancelling headphones and thus is very tolerable to youth. The participant will be monitored by heart rate, blood pressure, and oxygen saturation measurements, and will be able to communicate with the MRI technician and investigator immediately outside of the scanner. As BOLD is potentially influenced by O₂ delivery (ERPF) and O₂ consumption (tubular Na transport accounts a majority of renal O₂ consumption (103)) we will control for ERPF and fractional excretion of sodium (FeNa). We will perform the MRI after the clamp to remove the effects of acute variations in glycemia on RPF. Participants on medications that might alter O₂ delivery and/or consumption, e.g. angiotensin-converting enzyme inhibitors (ACE-I), angiotensin receptor blockers (ARBs) and diuretics will be excluded.

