Evidence of Benefit to Society: The importance of the knowledge gained from this protocol is high, since DKD is very prevalent in T1D and increases the risk of death from CVD and shortens lifespan. In fact, T2D in youth is increasing in prevalence in parallel with the obesity epidemic. In the United States, almost half of patients with renal failure have DKD. Despite the high prevalence and gravity of DKD in youth onset T1D, widely effective therapeutic options are lacking. Diabetes mellitus is the third most prevalent severe chronic disease of childhood. DKD remains a leading cause of morbidity and mortality, and a major risk factor for CVD in diabetes. Although data to guide care of DKD in adults with diabetes are limited, even less data exist regarding the antecedents of DKD in youth with diabetes. Yet, these antecedents of adult DKD are present in childhood, data to inform clinicians as to treatment in this high-risk population are of great public health importance. In our novel and innovative proposal, we postulate that coffee will decrease renal oxygen consumption, thereby improving renal oxygenation without impairing GFR and ERPF. Knowledge gained from this proposal will provide new information about the effects of coffee on renal energetics and intrarenal hemodynamic function in T1D. The investigative team is also unique in being one the few groups skilled in performing both gold standard renal physiology studies and advanced MRI evaluation in youth with T1D.

G. Data Analysis Plan (formulated with biostatistician [name] PhD):

Aim 1-2 Power calculations, statistical analysis, rigor and reproducibility: For this initial pilot and feasibility trial, we plan to recruit 10 youth. Power calculations are based on paired *t*-tests. A sample size of 10 provides 80% power to detect a mean paired difference of 0.44 SD for renal oxygenation and tubular injury markers. The following variables will be considered for inclusion in models as confounders: response: age, sex, ethnicity, T2D duration, HbA1c, BP, LDL-C and FeNa. We will use paired *t*-test and McNemar's test in addition to multivariable linear models of the change in each outcome, adjusted for potential confounders. This is a pilot and feasibility study and the data should be considered hypothesis generating. We acknowledge that we may be underpowered for multivariable modeling, and our primary analyses will be unadjusted.

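### FeNa measures the route by which coffee is expected to act on renal oxygenation, so it should not be treated as a confounder in the secondary R2* models

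*Combined protocol and SAP*

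**What the plan says.** **Mechanism.** II. Background and Significance says caffeine can lower renal oxygen use by inhibiting sodium "reabsorption which accounts for the majority of renal" oxygen consumption. Under E, Potential scientific problems, the expected result is: "We anticipate an increase in renal oxygenation due to decreased renal oxygen consumption with preserved GFR and ERPF in response to coffee therapy". FeNa, calculated from serum and urine sodium and creatinine, is the plan's measure of tubular sodium handling.

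**Adjustment.** The same part of section E notes that BOLD responds to oxygen delivery (ERPF) and to oxygen consumption (sodium transport), and concludes that "we will control for ERPF and fractional excretion of sodium (FeNa"). Section G is looser: "The following variables will be considered for inclusion in models as confounders". FeNa is one of the eight variables that follow; ERPF is not among them. The models are "multivariable linear models of the change in each outcome, adjusted for potential confounders", and "our primary analyses will be unadjusted".

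**Not stated.** The documents do not say whether FeNa enters as a baseline, post-visit or change value, or whether it is centred. They do not describe the FeNa-adjusted model as a mediation or direct-effect analysis.

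**The concern.** A confounder adjustment should remove influences other than coffee. Under the protocol's own hypothesis, the change in FeNa is part of what coffee does, so adjusting for it can remove the effect being sought. The adjusted R2* result could then shrink because the mechanism worked as expected, and be read as no effect after confounder adjustment. The pilot is meant to direct a larger trial, so that misreading could carry forward. Sections E and G also differ: one commits to the control, while the other only lists FeNa as a candidate and omits ERPF.

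**Working it through.** The documents give no figure to reproduce on this point. From them come n = 10, a single group without a control, and linear models of the change in each outcome. Everything else below is assumed: a total R2* change of -1.00 in residual SD units (the sign is immaterial), a mean FeNa change scaled to 1, a mediated share *m*, a reliability *r* of measured FeNa change, and the SD of FeNa change.

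**1. Where the coffee effect sits.** Fit ΔR2* = a + b·x + error. Everyone drinks coffee, so there is no coffee term and the intercept is read as the coffee effect. Least squares gives a = mean(ΔR2*) - b·mean(x).

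**2. x = change in FeNa, uncentred.** Let ΔR2* = -(1 - m) - m·d + error, where d is the true FeNa change with mean 1. The fitted slope is on average -m·r, so a = -1 + m·r = -(1 - m·r).

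| m | r = 1 | r = 0.5 |
|---|---|---|
| 0% | -1.00 | -1.00 |
| 25% | -0.75 | -0.88 |
| 50% | -0.50 | -0.75 |
| 75% | -0.25 | -0.63 |
| 100% | 0.00 | -0.50 |

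At m = 50%, r = 0.25 gives about -0.87 and r = 0.1 gives -0.95. Simulation (40,000 trials of n = 10 per setting) agrees with the formula. A two-visit model with subject fixed effects and time-varying FeNa gives a visit coefficient equal to this intercept.

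**3. x = mean-centred FeNa (baseline, post-visit or change).** mean(x) = 0, so a = mean(ΔR2*) = -1.00. Nothing is adjusted.

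**4. x = baseline FeNa, uncentred.** a = -1 - s·k, where s is the slope of the R2* change on baseline FeNa and k is the baseline mean in SDs above zero. This is a prediction at FeNa = 0. With k = 2, s = -0.3 gives -0.40, s = +0.3 gives -1.60 and s = 0 gives -1.00. The median 95% CI half-width is 1.68 at k = 2, against about 0.7 unadjusted. Steps 3 and 4 hold equally for baseline age, HbA1c or LDL-C.

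**5. A non-coffee shift in salt intake.** Suppose coffee raises FeNa by 0.5, R2* changes by -1 per unit of FeNa, the direct effect is -0.50, and a salt shift adds 0.2 to FeNa. The true coffee effect is -0.50 - 0.5 = -1.00. Unadjusted (or centred): -0.50 - (0.5 + 0.2) = -1.20. Adjusted for uncentred FeNa change: -0.50. Neither recovers -1.00. If coffee left FeNa unchanged, the direct effect would be the whole effect and the adjustment would remove only the salt shift.

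**6. Chance of p < 0.05, unadjusted / adjusted for uncentred FeNa change (r = 1).**

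| SD of FeNa change | m = 0% | m = 50% |
|---|---|---|
| 0.5 | 80 / 22% | 78 / 9% |
| 1 | 80 / 47% | 71 / 16% |

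At SD 0.5 the loss is 78 - 9 = 69 points with 50% mediation, but already 80 - 22 = 58 points with none. At SD 1 the losses are 55 and 33 points. Much of the loss is therefore imprecision from extrapolating at n = 10, not removal of a mediated effect.

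**The case against.** - **Only a secondary model is affected.** This stands. The unadjusted paired analysis is primary, the data are called hypothesis generating, and the plan concedes that multivariable models may lack power.
- **Beside age and HbA1c, baseline FeNa is a natural reading, and it is not a mediator.** This stands too: the loss in step 2 depends on a coding the plan does not specify. But baseline FeNa cannot confound a within-person mean change, so that reading leaves the confounder label without a purpose.
- **FeNa could absorb a drift in salt intake.** Coffee may start up to 30 days after the baseline visit, so drift is plausible. A reader might infer that no coding could ever yield an adjusted coffee effect. That is too strong: change in FeNa would serve if coffee did not alter FeNa. The protocol hypothesises the opposite.
- **Holding delivery and consumption fixed is legitimate physiology.** Agreed, provided it is declared as such. ERPF is a lesser concern: H2.1 states "Coffee drinking will not significantly change GFR and ERPF in youth with T1D", and if ERPF is indeed preserved, conditioning on it removes little.
- **The FeNa sample.** A reader might infer that furosemide contaminates FeNa. The documents do not support this. The 4-hour urine is assigned to albumin measures, serum sodium and creatinine are in the fasting draw, and fasting urine is taken with fasting blood. The text points to a fasting sample taken before furosemide, though the FeNa paragraph does not name it.
- **Visit order.** Section E says "We will perform the MRI after the clamp to remove the effects of acute variations in glycemia on RPF", while the visit descriptions put the MRI before the clamp. That contradiction is real but is a separate item.

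**Conclusion.** The point holds and is minor. Sections E and G treat a measure of the hypothesised mechanism as something to control for. If it enters as on-study change, the secondary R2* intercept loses the share acting through natriuresis: from none to all of the effect as mediation runs from 0 to 100%, and less if FeNa is noisy. The direction follows from algebra. The size rests wholly on assumed inputs, because the documents give no mediated share, reliability or FeNa distribution. If FeNa enters as a baseline or centred covariate, it does not adjust the mean change for confounding, and the same is true of the other baseline covariates.

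Two stronger readings should be avoided. The primary result is not compromised. Nor does the fall from 78% to 9% measure the harm of adjusting for a mediator, since 58 of those 69 points are also lost when nothing is mediated.

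**What to change.** 1. In section G, remove FeNa from the confounder list for the R2* models. The argument here does not reach the other outcomes.
2. In section E, replace the commitment to control with wording such as: *Changes in FeNa and ERPF will be reported beside the change in R2\*. Any R2\* model that conditions on either is an exploratory mechanistic (direct-effect) analysis, with time point and coding stated, and is not a confounder-adjusted coffee effect.* This also brings sections E and G into line.
3. Mean-centre any remaining covariates so that the intercept stays the average change.
4. As a clarification only, name the urine sample used for FeNa. Reconcile the MRI and clamp order between section E and the visit descriptions as a separate item.

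The cost is a few sentences and no data. The adjusted R2* table loses a planned covariate, and a non-coffee shift in sodium intake stays unadjusted and should be named as a limitation.
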